1. PURPOSE OF STUDY

Neuropsychiatric symptoms (NPS) are a distinctive set of behavioral disturbances that are prevalent in mild cognitive impairment (MCI) and Alzheimer's disease (AD), worsening of which, particularly, can accelerate patients' cognitive and functional decline and cause significant distress to caregivers.^{1,2} NPS often co-exist, rendering the need to understand the shared biological mechanisms underlying multiple NPS, which is crucial for the development of effective interventions to address them simultaneously. Notably, we recently discovered a neural circuit shared by MCI and AD patients with multiple NPS; the circuit is composed of 10 frontal-temporal-striatal regions³ and is highly related to both study partner-rated Neuropsychiatric Inventory Questionnaire (NPI-Q) and AD pathology (indexed by cerebrospinal fluid A β /ptau ratio).³ The **goal of this proof-of-concept mechanistic intervention study** is to confirm the causal relationship between this neural circuit and various NPS, by modifying a key region within the neural circuit [i.e. left precentral gyrus (LPG), critical for regulating visual attention⁴] with anodal transcranial direct current stimulation (tDCS).

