4. STUDY DESIGN

This is a Stage 0 study for mechanistic understanding. We will recruit older adults with study partner-rated NPS that has worsened in the past 2 years. Our previous study shows that this will capture

the most detrimental type of NPS.¹ We will focus on the MCI group, since understanding and modifying NPS among this group may assist in slowing the progression of dementia. See Table 1 for the overview of assessment and intervention timeline.

- Double-blind randomized controlled trial of 40 participants and their study partner subjects; all eligible and interested intervention subjects will be enrolled and undergo a baseline assessment, MRI scan, and blood draw; PI, staff conducting follow-up assessments and intervention subjects and their study partner subjects will be blinded. Interventionists and data managers will know randomization.
- After baseline, all intervention subjects will be randomly assigned to one of two groups - active anodal or sham C3 tDCS. A MATLAB block-based randomization code will be used to randomly assign study ID to group. Each study ID-group pairing will be printed and placed inside a sealed envelope labeled with only the study ID to ensure blinding. After an intervention subject and their partner subject finish baseline assessments, the interventionist or data manager will open the randomization envelope to assign the respective study ID.
- All intervention subjects will undergo a total of fourteen (14) 20-minute tDCS sessions over the course of four weeks: ideally, five times a week for two weeks, followed by twice a week for an additional two weeks. However, we will extend the intervention for additional two weeks for make-up sessions.
- Assessments will occur at baseline, within 2-week after finishing intervention (post-intervention assessment), and 4 to 6 weeks after post-intervention assessment (follow-up assessment).
- Unblinding will occur upon the completion of the follow-up assessment. We will not provide those in the sham group with the active tDCS procedure.

Primary endpoints:

- Resting-state and visual attention task-related fMRI;⁴⁵

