All intervention subjects will receive anodal tDCS stimulation or a sham intervention for 20 minutes per session, on C3 and the cathode electrode on Fp2 using 10/20 EEG system (**Figure C3B**). tDCS will be applied with a pair of 35 cm² single-use sponges soaked in approximately 4mL of saline solution on each side (~8mL per sponge) connected to the stimulator. During the 20-minute tDCS session, we will use online tDCS design (i.e., an intervention subject will simultaneously work on the visual attention-oriented task.

Active tDCS Condition: We will apply the stimulation for 20 minutes using current at 1.5mA with a ramp up and ramp down period of 30 seconds at the start and end of the session (Of note, the two 30 seconds are counted in the 20-minute session).

Sham tDCS Condition: tDCS will ramp up for 30 seconds with 1 mA current and then ramp off within 10 seconds. As 30 seconds is too short for tDCS to have any effects, this will be the sham condition. tDCS is on for 30-40 seconds because that is usually the only time individuals would experience tingling and itching – a factor we aim to equate between experimental and control conditions.

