17. DATA ANALYSIS PLAN

This is a pilot study for mechanistic understanding of the relationship between our previously discovered NPS-shared neural circuit and study partner-rated NPS. Results from the study will provide information for accurately calculating effect size for future clinical trial. Regardless, in addition to follow the rule of 12-20 subjects per group for a pilot clinical trial, we will calculate the sample size. The sample size calculation is based on the effect size of LPG related tDCS on visual attention performance ($f = 0.45$, $n = 36$). Additionally, the effect size of correlation between NPS-shared neural circuit and patient-report NPI-Q was $r^2 = 0.70$ in our previous study³ – here we use a much more conservative estimation at $r^2 = 0.20$, the sample size will be $n = 37$. All of these calculations are based on power at 0.80 and alpha at 0.05. For an 8-week follow up, we estimate 10% attrition rate. Therefore, we propose a total of 40 intervention subjects for the study.

Aim 1. Determine the effect of tDCS on NPS-shared neural circuit. H: After intervention, the active, relative to sham group will have greater increase in LPG activity, indexed by greater activation in LPG in response to visual attention task (H1a) and greater increase in resting FC strength between LPG and other regions within the NPS-shared neural circuit (H1b). To assess the activation pattern in LPG, we will conduct GLM analysis with the SPM software. The coefficients of GLM corresponding to LPG will be analyzed through hypothesis testing. We will first conduct a simple t-test to evaluate whether the intervention increases LPG activation for each group (at 4 or 8 weeks), and then a more powerful two sample kernel test will be used to test activations distribution difference between groups.⁵¹ Similarly, we will take the FCs between LPG and other regions as a multivariate covariate and apply the two-sample kernel test to evaluate group difference in the change of LPG FC pattern after intervention (at 4 or 8 weeks). In addition, simple multiple testing for each connection will be used as a screening procedure to identify a subset of connections included in the kernel test.

Aim 2. Determine the relationship between NPS-shared neural circuit and study partner-report NPS.

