H2a. After intervention, the active, relative to sham group will have greater improvement in study partner-rated NPS in terms of lower severity and fewer co-existing symptoms: We will fit linear mixed-effect models for changes in NPS: $Y_i = X_i\beta + Z_iu_i + \epsilon_i$, where $Y_i = (y_{i1}, \dots, y_{iT})$ represents the NPI measures across time, X_i is a $T \times p$ design matrix for the fixed effects and Z_i is a $T \times q$ matrix for the random effects. The models will include fixed effects such as data collection visit (categorical variable), group, visit and group interaction, and covariates identified as being imbalanced among groups. Stepwise variable selection based on Akaike Information Criteria will be used to select the fixed effects for inclusion. A random participant-specific effect will be included to account for correlation between visits for the same participant. The model-based average within-group change will be computed for each outcome at 4 and 8 weeks. This will allow us to rank the groups in terms of average within-person gains in each outcome. We will conduct a composite hypothesis test to assess if the changes at 4 or 8 weeks differ by groups (similar to a one-factor ANOVA but accounting for repeated measures). **H2b. FC change in NPS-shared neural circuit will contribute to the improvement in study partner-rated NPS across groups:** We will perform epsilon-intensive support vector regression (SVR) with RBF kernel using LIBSVM library.⁵² The Leave-One-Out-Cross-Validation scheme will be applied: each intervention subject will be designated as

the test sample once, while the remaining intervention subjects will be used as training sample. All training sample's features (change of voxel activation from the task or change of FCs from the NPS-shared neural circuit after intervention) will be trained to predict the test sample's outcome (change of NPI severity or frequency score). We will then perform model fitting of the raw and predicted NPI using linear function ($f(x)=ax+b$). Adjusted R^2 will be used to estimate goodness of fit for the model.

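### H1b: per-connection tests choose which LPG connections enter the active-versus-sham kernel test, the screen is not specified, and nothing accounts for the selection

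*Combined protocol and SAP*

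**What the plan says.** Section 4 (Study Design) lists "Resting-state and visual attention task-related fMRI" as the primary endpoint. Section 17, Aim 1, splits this into task activation (H1a) and resting connectivity of the LPG (H1b).

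For H1b the plan will "apply the two-sample kernel test to evaluate group difference in the change of LPG FC pattern after intervention". It then adds that "simple multiple testing for each connection will be used as a screening procedure to identify a subset of connections included in the kernel test".

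The plan does not say whether the per-connection tests compare active with sham, test change within each arm, or test change in all participants together. It gives no threshold or correction. H1b is introduced as parallel to H1a, where the plan says: "We will first conduct a simple t-test to evaluate whether the intervention increases LPG activation for each group". A within-arm change-from-baseline test is therefore one plausible form of the screen.

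No outside data are named for the screen, so the natural reading is that it runs on the trial's own participants. The one resampling safeguard in section 17 is under H2b: "The Leave-One-Out-Cross-Validation scheme will be applied". It covers the prediction model for NPI change and does not reach H1b.

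**The concern.** A two-sample kernel test takes its p-value from a null distribution in which the variables are fixed beforehand. If the same participants and the same group labels have already picked the connections, those connections tend to be the ones where the arms differ by chance. The kernel test then meets that chance difference again and counts it as new evidence.

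What is at stake is how one half of the primary endpoint is decided. If stimulation does nothing to LPG connectivity, H1b could look positive more often than the nominal level implies. A reader of the results could not tell from the plan whether the reported p-value is of this kind.

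**Working it through.** **Inputs from the document**

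- Participants: 40 randomised with 10% attrition (section 17), so 40 × 0.90 = 36. The allocation ratio is not stated; 1:1 is assumed, giving 18 per arm.
- Connections: section 1 says "the circuit is composed of 10 frontal-temporal-striatal regions", and the LPG is one of them, so 10 − 1 = 9.
- Level: alpha 0.05, stated only for the sample size. Sidedness is not stated, but the plan's correlation calculation reproduces as two-sided: ((1.960 + 0.842)/atanh(√0.20))² + 3 = (2.802/0.481)² + 3 = 36.9, so 37 as stated. One-sided would give 29.7.

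The plan gives no error rate for screening followed by the kernel test, so there is no figure of its own to reproduce for that step.

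**Assumptions**

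Normal change scores; equal correlation between connections of 0, 0.3, 0.5 or 0.7; kernel exp(−d²/median d²); 199 label permutations; an empty screen counts as not significant; 2,000 null datasets per setting. Monte Carlo standard error is about 0.5 points near 5% and 0.9 near 18%.

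**Step 1: how the inflation arises**

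With 9 uncorrelated connections and no effect, the chance that at least one passes p<0.05 is 1 − 0.95⁹ = 37.0%. In a simulation at correlation 0 the group screen selected something in 37.9% of datasets, and the kernel test then rejected in 18.6% of all datasets. That is 18.6/37.9 = 49% of those with a selection, where a valid test would reject in about 5%.

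**Step 2: overall false-positive rate (%) by type of screen**

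| Screen | corr. 0 | 0.3 | 0.5 | 0.7 |
|---|---|---|---|---|
| None, all 9 connections | 5.0 | 6.0 | 4.4 | 4.6 |
| Group comparison, p<0.05 | 18.4 | 17.6 | 12.0 | 7.2 |
| Change from baseline in either arm, p<0.05 | 18.1 | 15.0 | 10.8 | 7.6 |
| Group comparison, Bonferroni (9 tests) | 5.0 | 4.4 | 2.6 | 2.1 |
| Either arm, Bonferroni (18 tests), both arms change alike by 0.3 SD | 10.1 | 10.0 | 8.6 | 6.6 |

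Further results:

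- Active arm only, p<0.05: 4.8–9.6%.
- Either arm, Bonferroni, neither arm changes: 1.3–2.8%.
- Group-blind pooled screen: 1.1–2.0%.
- Looser group screen at p<0.20: 32.8% at correlation 0 and 9.1% at 0.7.
- Other kernels with the p<0.05 group screen (800 datasets per correlation): 7–12% for a narrow Gaussian, 18–32% for a linear kernel.

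The last row of the table matters because a shared change is plausible: in both arms, during each session, "an intervention subject will simultaneously work on the visual attention-oriented task". When both arms truly change, many connections come near the within-arm threshold. Those that cross it in one arm are partly those where that arm is high by chance. The 0.3 SD is an assumption.

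**Step 3: reading the kernel p-value alone**

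After a Bonferroni group screen the overall rate is controlled because the screen rarely selects anything. When it does, the kernel test rejects in about 9 of 10 null datasets (small counts, about 50–100 per setting). The kernel p-value then adds almost nothing to the screen.

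**Step 4: do the remedies hold the level?**

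All 9 connections with no screen: 4.4–6.0% (table). Either p<0.05 screen (group or either-arm) repeated inside every permutation: 4.0–5.8%, with or without the shared change. A second set of runs with the group screen nested gave 4.4–6.4%.

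**Step 5: effects on selected connections**

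With 18 per arm, passing a p<0.05 group screen needs an observed difference of at least t(0.975, 34) × √(2/18) = 2.032 × 0.333 = 0.68 SD.

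**The case against.** The strongest reply is that the harm depends on facts the plan leaves open. Multiple testing may be meant to include a correction, and a corrected group comparison or a group-blind screen leaves the overall error at or below about 5%. This stands: the document shows an unspecified step, not a test shown to be invalid. It does not remove the point, because no correction is stated and one corrected screen, the either-arm version, can still inflate.

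A second reply is that the kernel test is first described on the LPG connections as a whole, and the screen arrives as an addition. An unscreened main test with a screened supplement is possible. That would be close to the first remedy below, but the sentence says the subset is what goes into the kernel test, so the screened reading is the more natural one.

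Third, this is a Stage 0 pilot for mechanism. That tempers severity, but fMRI is still the listed primary endpoint.

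A reader might also infer that inflated effects from screened connections will size the next trial, since the plan says "Results from the study will provide information for accurately calculating effect size for future clinical trial". The document does not support this. It does not say which effect size is meant, and section 1 describes the future trial as one addressing NPS, so the relevant effect may be on the NPI.

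**Conclusion.** The point holds in a conditional form. Section 17 lets per-connection tests select the input to the H1b kernel test, does not specify the screen, and does not account for the selection. If the screen uses the group labels, a kernel p-value that takes the selected connections as given is not valid on its own.

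Under the stated assumptions, the overall false-positive rate is about 7–18% for an uncorrected group or either-arm screen and about 5–10% for an active-arm-only screen. It is 6.6–10.1% for a Bonferroni either-arm screen with a shared 0.3 SD change. Other kernels or looser thresholds can take the group screen to about 30%. These figures are illustrative: the 18 per arm, normality, equal correlation and kernel are all assumed.

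Two stronger readings are tempting and not supported. One is that any screen using the labels inflates error by a large, fixed factor; the active-arm-only screen shows little or no inflation at its lower end. The other is that lack of correction is the whole problem, so that adding one settles it. A corrected group comparison protects the overall decision, but a corrected within-arm screen need not.

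This should be fixed before unblinded analysis. Confidence is medium, because the size depends on a screen the plan does not describe.

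**What to change.** State in section 17 that H1b is decided by one permutation p-value, obtained in one of two ways:

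- (a) the kernel test on all 9 LPG connections with no screen, with per-connection results reported as multiplicity-adjusted follow-up; or
- (b) a screen whose contrast and threshold are fixed in advance and which is repeated inside every permutation of the group labels, with the statistic set to zero when nothing is selected.

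If effect sizes from screened connections are reported, label them as selected and likely too large.

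The cost is wording, some computing and some power; no new data are needed. The choice between (a) and (b) turns on the expected pattern of change. Simulated power (1,000 datasets per setting, correlation 0.3 / 0.5; the range for (b) covers the group and either-arm p<0.05 screens):

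| True change | (a) all 9 | (b) nested screen |
|---|---|---|
| One connection, 1.0 SD | 0.41 / 0.38 | 0.46–0.55 / 0.53–0.59 |
| Three connections, 0.6 SD | 0.40 / 0.32 | 0.30–0.32 / 0.27–0.29 |
| All nine, 0.6 SD | 0.72 / 0.54 | 0.45–0.56 / 0.37–0.43 |

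Option (a) loses power if a single connection changes; option (b) loses it if change is spread over several.

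### As listed, the H2a mixed model tests a raw difference in NPI change, which is valid but uses the collected baseline inefficiently; baseline adjustment should be pre-specified and protected from stepwise selection

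*Combined protocol and SAP*

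**What the plan says.** Section 17 (Data Analysis Plan), Aim 2, H2a, specifies linear mixed models whose outcome vector "represents the NPI measures across time". The mean model has "fixed effects such as data collection visit (categorical variable), group, visit and group interaction", together with "covariates identified as being imbalanced among groups". The plan then adds: "Stepwise variable selection based on Akaike Information Criteria will be used to select the fixed effects for inclusion". For the covariance: "A random participant-specific effect will be included to account for correlation between visits for the same participant".

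Two results are taken from the model. The first is descriptive: "The model-based average within-group change will be computed for each outcome at 4 and 8 weeks". The second is the between-arm test: "We will conduct a composite hypothesis test to assess if the changes at 4 or 8 weeks differ by groups".

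Section 8 and Table 1 show the full NPI being taken from the study partner at secondary screening and again at both post-intervention assessments. For enrolled participants the screening values stand as baseline. Section 4 places randomisation after baseline and lists partner-rated NPS as a secondary endpoint. Baseline NPI is not named as a covariate in section 17. Nor does it appear among the partner demographics that section 4.1 offers as controls for NPI, or the medication changes that section 4 treats as confounders.

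**The concern.** Change at 4 and 8 weeks can be computed from a model with categorical visit only if baseline is one of the outcome visits. Visit, group and their interaction then give every arm-by-visit cell its own mean, including a separate baseline mean in each arm. Randomisation after baseline makes those two baseline means equal in expectation, so estimating both spends information that could go to the treatment contrast.

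Precision matters here. About 36 completers are expected, no power is stated for H2a, and section 17 says the pilot is meant to supply effect sizes for a later trial. A wider interval than the data require works against that purpose.

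**Working it through.** **Inputs from the documents.** 40 participants, 10% attrition, two arms; alpha 0.05 and power 0.80 in the sample-size paragraph. Completers: 40 x 0.90 = 36, or 18 per arm if allocation is 1:1 (the ratio is not stated).

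**The plan's own figure.** The total of 40 follows from 36/0.90 = 40. The other component, n = 37 for r² = 0.20, is reproduced by the Fisher z formula (36.9, two-sided). Neither concerns the H2a contrast, so there is no stated H2a figure to reproduce.

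**Assumptions.** Equal NPI standard deviation (SD) at each visit; correlation rho between baseline and one post-baseline visit. The documents give neither an NPI SD nor rho, so results are in SD units for rho from 0.3 to 0.8.

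**Step 1: what the listed model estimates.** In 300 simulated complete-data trials (36 participants, 3 visits, rho 0.6, random intercept), the visit-by-group coefficient equalled the raw difference in mean change to within 2e-15.

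**Step 2: variance of the two contrasts, n per arm.**
- Difference in change: (2/n) x 2(1 - rho)
- Baseline-adjusted: (2/n) x (1 - rho²)
- Ratio, adjusted to change: (1 + rho)/2; its inverse is 2/(1 + rho)

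**Step 3: numbers at n = 18.** For example, at rho 0.3 the standard error (SE) for change is sqrt(2 x 0.7 x 2/18) = 0.394, and adjusted it is sqrt(0.91 x 2/18) = 0.318. The detectable difference is (1.960 + 0.842) x SE, for 80% power, two-sided 0.05, normal approximation.

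| rho | SE, change | SE, adjusted | Variance cut | Detectable difference (SD), change to adjusted |
|---|---|---|---|---|
| 0.3 | 0.394 | 0.318 | 35% | 1.10 to 0.89 |
| 0.5 | 0.333 | 0.289 | 25% | 0.93 to 0.81 |
| 0.7 | 0.258 | 0.238 | 15% | 0.72 to 0.67 |
| 0.8 | 0.211 | 0.200 | 10% | 0.59 to 0.56 |

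For comparison, ignoring baseline altogether gives sqrt(2/18) = 0.333. Subtraction beats this above rho 0.5, matches it at 0.5 and is worse below.

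**Step 4: small-sample check.** In 8,000 simulated trials per setting at 18 per arm, the variance ratio was about 0.67, 0.78 and 0.87 to 0.89 at rho 0.3, 0.5 and 0.7, against 0.65, 0.75 and 0.85 from the formula. The false-positive rate was about 5% for both methods. In the 300 trials of step 1, a common baseline mean gave a ratio of 0.73 and covariate adjustment 0.74. The formula gives 0.80 at rho 0.6, which is compatible given only 300 trials.

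**Step 5: does the imbalance clause help?** A covariate that is constant over visits and enters as a main effect does not move a within-person contrast when data are complete. In one simulated trial the contrast was -0.0647 without covariates, with an added covariate, and with baseline NPI itself added.

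**Step 6: what stepwise AIC can do.** AIC drops a 2-df term when its likelihood-ratio statistic is below 4. With no treatment effect, in large samples, that has probability 1 - exp(-2) = 0.86 for the visit-by-group term. Selection may instead drop the group main effect, which would give a common baseline mean, but only by accident of the data.

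**The case against.** The strongest reply is that nothing here is invalid, and that stands. Three stronger readings are tempting, and the documents support none of them.

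- A reader might infer that baseline is not used at all. It is used, by subtraction, and above rho 0.5 this improves on ignoring it (0.258 against 0.333 at rho 0.7).
- A reader might infer that the effect is biased. Over randomisations it is not. A chance baseline difference of x shifts the expected contrast by (1 - rho)x in the opposite direction, but only conditional on that imbalance, and the SE already allows for it. With 20 per arm, a difference above 0.5 SD has probability 0.11 (SE sqrt(2/20) = 0.316).
- A reader might extend the point to H1b, where the plan will "evaluate group difference in the change of LPG FC pattern after intervention". That is a multivariate kernel test of distributions. The ratio above is for a single mean contrast and has not been shown to carry over, so no claim is made about H1b.

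It can also be said that baseline as an outcome is inferred, not stated. If the outcome were post-baseline change, the imbalance clause could bring in baseline NPI as a useful covariate. That reading fits the words on NPI measures over time less well, and adjustment would then depend on an imbalance being noticed. The list of fixed effects is itself open-ended and subject to AIC, so the final model is not determined. That is an argument for fixing it in advance.

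Finally, NPS is a secondary endpoint in a mechanistic pilot. This limits the stakes, but the remedy needs no new data.

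**Conclusion.** The point holds as a loss of efficiency in H2a. As listed, the model yields the raw difference in NPI change, exactly so with complete data and approximately so with the expected 10% attrition. Its variance for one post-baseline visit is 2/(1 + rho) times that of a baseline-adjusted contrast. The avoidable share is about 35% of the variance at rho 0.3, falling to 10% at rho 0.8, and slightly less at 18 per arm.

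The size rests on an assumed rho, equal SDs across visits and 1:1 allocation. Any power figure is illustrative only. The plan's f = 0.45, equivalent to 0.9 SD for two equal groups, refers to visual attention performance, and the documents give no NPI effect size.

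The AIC step makes the matter more pressing, because the terms that carry the treatment comparison are themselves open to removal.

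**What to change.** In section 17, Aim 2 (H2a) only:

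1. Pre-specify one of two models. Either fit the mixed model to the two post-baseline full-NPI visits with visit, group, visit-by-group, baseline NPI and baseline-by-visit as fixed effects; or keep baseline as an outcome and constrain both arms to one common baseline mean.
2. State that these terms are always retained and are exempt from stepwise AIC selection.
3. Report the active-minus-sham difference at each post-baseline visit with a 95% CI.

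The cost is SAP wording and model code. The covariate form drops only participants with no post-baseline NPI.
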